Enhancing the Acceptability of Psychological Treatments for
Obsessive-Compulsive Disorder

Study Protocol and Statistical Analysis Plan

Unique Protocol ID: 30006258

Date: July 20, 2018

Study Protocol

Individuals who contact the clinic expressing interest in the study will first complete a telephone screen in order to assess their potential eligibility. Screener questions from the ADIS-V will be used to determine their likely inclusion in the study; those who seem likely to be eligible will be invited to the clinic to complete a baseline assessment, consisting of the ADIS-V and YBOCS, as well as measures of OCD, anxious and depressive symptomatology and demographic and treatment history measures.

We will administer several measures to assess treatment acceptability. These will include the Credibility/Expectancy Questionnaire (CEQ), and the Treatment Acceptability / Adherence Scale (TAAS). The CEQ and TAAS will serve as subjective measures; objective measures will include counts of treatment refusers and dropouts across the two treatments. A refuser is defined as a participant who is deemed eligible following the initial assessment, but who declines to continue at any time after randomization, but before session 2 (the first session is for case formulation, treatment planning, and includes a comprehensive description of the treatment approach). A dropout is defined as a participant who withdraws their participation from the study any time after the beginning of session 2. Should any participant refuse or drop out of CT or ERP, we will ask them to list their reasons for this decision.

In addition to the Anxiety Disorders Interview Schedule (ADIS-V), we will administer the Yale-Brown Obsessive-Compulsive Checklist (YBOCS). Diagnostic and interview reliability will be assessed via a second trained rater who will listen to and rate recordings of interviews. In instances where there is disagreement on diagnostic status, a team meeting will be held to discuss the issues and resolve the discrepancy. Self-report measures assessing OCD symptoms (i.e., Vancouver Obsessional Compulsive Inventory, VOCl), OCD beliefs (Obsessional Beliefs Questionnaire, OBQ), process measures (e.g., Personal Significance Scale, PSS), as well as measures of depression and anxiety symptomatology (Beck Depression Inventory, 2nd Ed, BDI & Beck Anxiety Inventory, BAI) will be administered.

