Eligible participants will be block randomized (to ensure equal numbers of participants per treatment condition) via www.randomizer.org, and will begin session 1 of either ERP or CT with one of 2 therapists (see below). Participants will be asked to complete the PSS and VOCl before the start of each session. At all time points, assessors will be blind to treatment assignment, such that they will not know whether a participant has been offered or is receiving ERP or CT. After the 3rd, 6th, and 12th and final session, and at each follow- up point, participants will be asked to complete the CEQ and TAAS in order to assess their views of the acceptability of the treatment they receive. After session 6, participants will complete a mid-therapy assessment consisting of the YBOCS, VOCl, OBQ, PSS, BAI and BDI.

This RCT will involve trial administration (shared by the Investigators and the study coordinator), an assessment team (research assistant and graduate student), and a team of 3 therapists (post-doctoral fellow(s) and a senior graduate student). This will allow for comparisons of therapist effects, as well as the effects of therapist experience on outcome and acceptability. The first 6 months of the project are reserved for training team members on relevant tasks. Training will be overseen by the NPA, and offered by all project investigators.

ERP (12 sessions) will be based on a standard, commonly-used manual, and will comprise 1 session of case formulation and treatment planning, 10 sessions of ERP, plus 1 final session on relapse prevention. Exposures in this protocol are prolonged and repeated, requiring clients/patients to engage in a series of exposures to feared stimuli (e.g., contaminants, doubts, intrusive thoughts), and to refrain from engaging in compulsive behaviour until their anxiety subsides. ERP is well-established, and known to be highly effective for OCD.

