CT (12 sessions) will be modularized, and based on elements from our three primary treatment packages. It will begin with 1 session of case formulation and treatment planning, followed by 10 sessions focused on evidence gathering and behavioural experiments (which are importantly different from prolonged exposure), plus 1 final session on relapse prevention. The 3 treatment packages share a number of common features – they include focus on reducing inflated responsibility, target the personal significance of the participant's thoughts or compulsions, etc. Each also incorporates other elements specific to the primary symptom (e.g., beliefs about memory in compulsive checking, a perceived violation in mental contamination, or thought-action fusion in association with obsessions), allowing CT to be tailored to the individual beliefs and concerns of each participant. Many of these cognitive areas of focus are highly novel, and have not been assessed in previously conducted RCT's of CT, although our focus on problematic beliefs and appraisals in general is entirely consistent with established CT for OCD packages.

All sessions will be recorded in situ for the purposes of assessing treatment fidelity; this will be done on an ongoing basis via trained coders, blind to hypotheses and to condition assignment who will be asked to assess the proportion of session content allocated to a focus on behaviour/exposure vs. cognition/reappraisal. Audio recording devices will be made available to participants and their use is a standard enhancement of treatment interventions to help make them more memorable, and to clarify any questions that may arise between sessions.

At the end of treatment, and at 6- and 12-month follow-up periods, participants will complete the mid-therapy assessment measures again, in addition to the ADIS-V.

Statistical Plan

Primary hypotheses will be tested by comparing our indices of acceptability across the two treatments. Specifically, participant ratings of treatment acceptability, and the relative numbers of treatment refusers and dropouts will be assessed. Independent samples *t*-tests will be used to compare the two treatments groups on self-reported treatment acceptability on the CEQ and the TAAS. Furthermore, chi-squared tests will be used to compare treatments on the number of refusers and drop outs.

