Completer and intent-to-treat analyses will be conducted on YBOCS and VOCI total scores (i.e., OCD symptom severity) measured at multiple time points. ANCOVA will compare treatments on changes in OCD symptom severity across all measurement periods, with baseline scores as covariates. Although we have reason to suspect that our CT may outperform more traditional cognitive approaches to the treatment of OCD, we expect that both ERP and CT will be similarly effective (as has been shown in numerous trials, and in a recent comprehensive review), perhaps with intent-to-treat analyses showing a small advantage of CT over ERP, yet we do not expect to be powered to detect significant differences.

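### The plan provides for no YBOCS or VOCI after a participant refuses or drops out, so an intent-to-treat CT advantage could not be separated from differential dropout

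*Combined protocol and SAP*

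**What the plan says.** **Assessment schedule (Study Protocol).** YBOCS is taken before randomisation, when likely-eligible people are "invited to the clinic to complete a baseline assessment, consisting of the ADIS-V and YBOCS". The next is tied to a session: "After session 6, participants will complete a mid-therapy assessment consisting of the YBOCS, VOCl, OBQ, PSS, BAI and BDI". The rest are tied to the end of therapy and to follow-up: "At the end of treatment, and at 6- and 12-month follow-up periods, participants will complete the mid-therapy assessment measures again". VOCI is taken at these points and also before every session. No session frequency or treatment duration is given, and no starting point is stated for the 6 and 12 months.

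**Leavers (Study Protocol, acceptability measures).** A refuser is an eligible participant "who declines to continue at any time after randomization, but before session 2". For the other group: "A dropout is defined as a participant who withdraws their participation from the study any time after the beginning of session 2". One request is made of both: "Should any participant refuse or drop out of CT or ERP, we will ask them to list their reasons for this decision". No symptom measure is mentioned.

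**Analysis (Statistical Plan).** Refusal and dropout counts are among the primary acceptability comparisons. YBOCS and VOCI totals are to be compared by ANCOVA, in completer and intent-to-treat form. The authors expect the two treatments to work about equally well, "perhaps with intent-to-treat analyses showing a small advantage of CT over ERP", and do not expect adequate power for a difference. How missing scores enter the intent-to-treat analysis is not stated.

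**The concern.** An intent-to-treat comparison asks how everyone assigned to CT fared against everyone assigned to ERP. If completers do about equally well, a CT advantage seen only in that analysis has to come from those who left. The plan makes no provision for scoring those people after they leave.

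The missing part of the estimate would then be supplied by whatever rule fills the gaps. Because leaving is itself a primary outcome, the symptom result could partly repeat the refusal and dropout result in YBOCS points and be read as separate evidence that CT reduces symptoms more. An analysis method can be specified later, but scores that were not collected cannot be recovered.

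**Working it through.** **Step 1. Which scores exist under the plan as written**

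| Participant | YBOCS | VOCI |
|---|---|---|
| Refuser (leaves before session 2) | Baseline only | Pre-treatment only (at most the one before session 1) |
| Dropout before the session-6 assessment | Baseline only | Up to last session attended |
| Dropout after it | Baseline and session 6 | Up to last session attended |
| Any of these, after leaving | No provision | No provision |

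**Step 2. Inputs for an illustration**

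The documents give no sample size, leaving rate or expected gain, so there is no figure of the plan's own to reproduce. Every value here is an assumption: completers in both arms gain G = 10 YBOCS points; pE = 30% leave ERP and pC = 15% leave CT; leavers in both arms gain d = 0, 4 or 8 points.

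**Step 3. True difference by assignment (CT minus ERP gain)**

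[(1 − pC)G + pC·d] − [(1 − pE)G + pE·d] = (pE − pC)(G − d)

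- d = 0: 0.15 × 10 = 1.5
- d = 4: 0.15 × 6 = 0.9
- d = 8: 0.15 × 2 = 0.3

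**Step 4. What the analysis would return, whichever of these is true**

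- Baseline carried forward: (pE − pC)G = 0.15 × 10 = 1.5.
- Last YBOCS carried forward, if a share f of leavers has a session-6 score showing half the full gain: (pE − pC)G(1 − 0.5f). This is 1.5 for f = 0, 1.125 for f = 0.5 and 0.75 for f = 1.
- Observed final scores only: 10 − 10 = 0, given that completers gain equally.

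Each method in effect assigns leavers a gain: 0 for baseline carried forward, 5f for last score carried forward, and 10 for observed scores only. None uses information on what happened after exit. A simulated ANCOVA (200,000 per arm, leaving independent of outcome, f = 0.5, no true difference) agreed, with apparent CT advantages of 1.49, 1.12 and about 0.

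**Step 5. Range**

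- With 25% v 15% leaving, the true values are 0.10 × 10 = 1.0, 0.10 × 6 = 0.6 and 0.10 × 2 = 0.2. Baseline carried forward gives 1.0, and observed scores give 0.
- With G from 8 to 12 and a gap in leaving of 10 to 20 percentage points, baseline carried forward gives 8 × 0.10 = 0.8 up to 12 × 0.20 = 2.4. Last score carried forward gives 8 × 0.5 × 0.10 = 0.4 up to 2.4.
- With equal leaving rates, every method gives 0.

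**The case against.** Three stronger readings are tempting, and the documents do not support them.

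- *Leavers contribute no symptom data.* All have a baseline YBOCS, those who leave after session 6 should have the mid-therapy one, and VOCI, the other severity outcome, is taken before each session. The gap is in scores after exit.
- *Leaving therapy ends data collection by rule.* Only the dropout definition refers to leaving the study. The refuser definition does not, and the request for reasons speaks of leaving the treatments. The follow-up sentence excludes nobody. The plan is silent, which is weaker than a prohibition, but an intent-to-treat analysis needs a stated collection rule.
- *An intent-to-treat CT advantage would merely restate dropout.* That is exact only for baseline carried forward with equal gains among completers. It is diluted when session-6 scores are used, and the plan names no method. Likelihood methods or multiple imputation would remove it if leaving depends only on observed scores, but that assumption cannot be tested without post-exit scores.

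A further point stands: a difference produced by leaving is not always wrong. If leavers gain nothing, 1.5 points is the true effect by assignment. The difficulty is that the data could not show whether this or a smaller value is the truth.

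The stakes are also limited. The primary hypotheses concern acceptability, the authors hedge the expected advantage and disclaim power, and reporting both completer and intent-to-treat results would show when a difference appears only in the latter. That reveals the pattern without explaining it.

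**Conclusion.** The concern holds as a gap in data collection, together with an unstated missing-data method. As written, the plan has no YBOCS or VOCI after exit and no assessment dates for people who stop early, so an intent-to-treat CT advantage could not be separated from differential dropout.

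On the main assumed values, the result would lie between 0 and 1.5 YBOCS points according to method alone, against a true difference of 0.3 to 1.5 depending on how leavers fare. These sizes rest on equal gains among completers, the same leaver gain in both arms, and assumed leaving rates. The conclusion that the two cannot be separated does not depend on the particular values, provided the arms differ in leaving. Because symptom severity is not the primary question, this is a worthwhile improvement and not a flaw in the main acceptability comparisons.

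**What to change.** **Study Protocol**

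- Record stopping therapy separately from withdrawing from assessment.
- Invite every randomised participant, including refusers and dropouts, to the mid-therapy, end-of-treatment, 6-month and 12-month YBOCS and VOCI, unless they decline assessment.
- Keep the present timing for people still in therapy. Set leavers' dates by a stated calendar, counted from randomisation or session 1 and matched to the planned session schedule. That schedule has to be written down first, since no session frequency is given.

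**Statistical Plan**

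- State how missing scores are handled for those who still decline, and add a sensitivity analysis that varies the gain assumed for leavers.

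**Cost**

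Protocol and consent wording, plus extra interviews for the existing assessment team. If 50 per arm are randomised and 30% and 15% leave (all assumed), that is 50 × 0.30 + 50 × 0.15 = 22.5, or about 22 people. At up to four assessments each, this is at most about 22 × 4 = 88 interviews. Some leavers will decline, so the gap shrinks without closing. If telephone interviews are offered, the mode should be recorded: the protocol uses the telephone only for screening, and using it mainly for leavers would tie interview mode to dropout.

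### CEQ and TAAS are rated repeatedly but compared only by t-tests with no stated occasion or missing-rating method; a late t-test can be biased by selective dropout, and a single early one wastes data

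*Combined protocol and SAP*

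**What the plan says.** The Study Protocol sets the rating schedule: "After the 3rd, 6th, and 12th and final session, and at each follow- up point, participants will be asked to complete the CEQ and TAAS". The follow-up points are at 6 and 12 months, so there are five scheduled ratings per scale, three of them during therapy.

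Under the primary hypotheses, the Statistical Plan states that independent-samples t-tests "will be used to compare the two treatments groups on self-reported treatment acceptability on the CEQ and the TAAS". It does not say which rating is tested, whether ratings are combined, who is analysed, or what happens when a rating is missing. Completer and intent-to-treat analyses are named only for the symptom scores (YBOCS and VOCI).

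A dropout is someone who "withdraws their participation from the study any time after the beginning of session 2", so a participant can rate at session 3 and then leave. A refuser "declines to continue at any time after randomization, but before session 2" and so leaves before the first scheduled rating. Leaving is compared separately, also under the primary hypotheses: "chi-squared tests will be used to compare treatments on the number of refusers and drop outs".

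**The concern.** An independent-samples t-test takes one score per person. If that score is the session 6 or session 12 rating, people who rated earlier and then left contribute nothing, although their earlier ratings say something about what they would have reported later.

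The protocol treats low ratings and leaving as two indices of the same thing, acceptability, and expects to compare both between arms. It is therefore plausible, though not established, that low raters leave and that they leave one arm more than the other. The arm that loses more low raters then keeps a more favourable group, and the comparison on the scale shifts in that arm's favour.

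Testing session 3 alone avoids this among those who rated, but sets aside every later rating. What is at stake is the estimate and the power of a primary comparison.

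**Working it through.** The plan gives no sample size, SD, alpha, effect size, correlation or dropout rate, so there is no figure to reproduce.

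**From the documents:** 1:1 block randomisation; in-therapy ratings after sessions 3, 6 and 12; t-tests for CEQ and TAAS; dropout possible from session 2 onward.

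**Assumed:** SD 1; two-sided alpha 0.05; the same true CT-ERP difference at each session (positive favours CT); within-person correlation of ratings 0.5 to 0.7; the dropout rates given below.

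**Step 1: direction and size of bias in a session 12 t-test on those still present.** Let dC and dE be the proportions leaving CT and ERP after session 3, s the correlation of leaving with a low session 3 rating, ρ the session 3-to-12 correlation, φ the standard normal density and z(d) the standard normal quantile of d.

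bias = ρ × s × [φ(z(dC))/(1 − dC) − φ(z(dE))/(1 − dE)]

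- CT 10%, ERP 30%: the two terms are 0.195 and 0.497, difference −0.302. With ρ = 0.7 and s = 0.6, bias = 0.42 × (−0.302) = −0.127. A true difference of 0.50 becomes 0.37.
- Over s = 0.3 to 1 and ρ = 0.5 to 0.7, bias runs from −0.05 to −0.21 for 10%/30% and from −0.02 to −0.11 for 15%/25%.
- Equal loss of 20% in each arm: bias 0, even when low raters leave.
- s = 0 (leaving unrelated to ratings): bias 0, even at 10%/30%.
- CT 30%, ERP 10%: bias +0.127, so 0.50 becomes 0.63.

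**Step 2: simulation of the same set-up** (4,000 runs, 50 per arm, true difference 0.50, ρ = 0.7, s = 0.6, CT 10%/ERP 30%).

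| Analysis | Mean estimate | Power |
|---|---|---|
| Session 12 t-test, those present | 0.37 | 38% |
| Session 12 likelihood estimate using session 3 ratings | 0.50 | 63% |
| Session 3 t-test | 0.50 | 71% |

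With the same dropout rates but leaving unrelated to ratings, the session 12 t-test gives 0.50 with 59% power. Most of the power lost in the first row is therefore due to bias, not to smaller numbers.

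**Step 3: simulation with all three ratings** (40 per arm, true difference 0.40, leaving after sessions 3 and 6 driven by the last rating, loss by session 12 about 17% CT and 36% ERP).

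| Analysis | Mean estimate | Power |
|---|---|---|
| Session 12 t-test, those present | 0.27-0.31 | 19-23% |
| Likelihood model, session 12 | 0.40 | 34-35% |
| Session 3 t-test | 0.40 | 42-44% |
| Likelihood model, average of three ratings | 0.40 | 49-55% |

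**Step 4: closed-form check without dropout**, at 40 per arm and difference 0.40.

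- One rating: SE = √(2/40) = 0.224; 0.40/0.224 = 1.79; power ≈ Φ(1.79 − 1.96) = 43%, in line with the session 3 row.
- Mean of three ratings: variance (1 + 2r)/3, which is 0.67 at r = 0.5 and 0.80 at r = 0.7. SE = √(2 × 0.67/40) = 0.183 and √(2 × 0.80/40) = 0.200; power ≈ Φ(2.19 − 1.96) = 59% and Φ(2.00 − 1.96) = 52%. Dropout brings these down to the simulated 49-55%.

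**The case against.** The strongest reply is that the plan never commits to a late rating. A session 3 t-test, one t-test per occasion, or a t-test on each person's mean rating would all use ratings from later leavers. This stands. A reader might infer that the planned t-tests necessarily discard leavers' earlier ratings and that unequal dropout will hide a CT-ERP difference. The documents do not support that. They name no occasion and give no dropout rate. Understatement needs loss that is unequal, related to ratings and heavier in the less acceptable arm, and in the adverse cases run here the difference shrinks but does not vanish.

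It is also fair to say that the power gain comes mainly from using all the ratings, not from the mixed model as such. In simulations with similar assumed dropout, a t-test on each person's mean of available ratings estimated 0.40-0.43 against a true 0.40, with 51-58% power at 40 per arm, about the same as the model's average. And at session 12 alone the model has less power than a session 3 t-test. The model's advantages are session-specific estimates that are unbiased when leaving depends on observed ratings, and a single stated rule for missing ratings.

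Third, unequal leaving would show in the chi-squared comparison, which is itself a primary test. That makes attrition visible, but it does not correct the CEQ and TAAS estimates.

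Finally, participants rate the treatment they receive, so a session 12 contrast that projects ratings for people who have left is open to question. That should be acknowledged when the contrast is defined.

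**Conclusion.** The point holds in conditional form. The firm defect is that two primary scales with repeated ratings have a single-score test and no stated occasion, analysis set or missing-rating method. Whether bias follows depends on which rating is tested and on who leaves.

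If a session 12 score is tested, and dropout is unequal and related to ratings, the illustration at 17%/36% loss understates a 0.40 SD difference by 0.09 to 0.13 SD (0.40 − 0.31 and 0.40 − 0.27). With the split reversed, a late test overstates the difference. With dropout unrelated to ratings there is no bias. A session 3 t-test is unbiased among those who rated, but at 40 per arm has 42-44% power against 49-55% for the three-rating average.

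All sizes rest on assumed sample size, SD, correlation and dropout, and on a constant difference across sessions. The simulated leaving depends on observed ratings, which favours the likelihood model.

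**What to change.** In the Statistical Plan, replace the CEQ and TAAS t-tests as the primary analysis with one mixed model for repeated measures per scale:

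- Outcomes: the ratings after sessions 3, 6 and 12.
- Terms: treatment, session and treatment-by-session, with unstructured covariance.
- Analysis set: every randomised participant with at least one rating, in the assigned arm.
- Primary contrast: the CT-ERP difference averaged over the three ratings.
- Supportive: the difference at each session with a 95% interval.
- Sensitivity: t-tests, with the occasion or summary named.

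The cost is SAP wording and a standard model; no new data are needed. The model has two limits. It assumes that leaving depends on observed ratings: where leaving depended on the unseen current rating (50 per arm, true 0.40), the model gave 0.31 and the t-test 0.24, so bias shrank but remained. It also cannot recover refusers or early dropouts who have no rating, and the plan should say so. The follow-up ratings lie outside this model and need their own stated analysis.

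### Does the non-primary symptom comparison need a pre-named lead estimate, an interval and a rule for reading a non-significant result?

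*Combined protocol and SAP*

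**What the plan says.** The Statistical Plan puts the primary hypotheses on acceptability: "Primary hypotheses will be tested by comparing our indices of acceptability across the two treatments". These indices are the CEQ and TAAS ratings together with refusal and dropout, for which "the relative numbers of treatment refusers and dropouts will be assessed".

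Symptom severity comes afterwards. "Completer and intent-to-treat analyses will be conducted on YBOCS and VOCI total scores", and the between-treatment method is one sentence: "ANCOVA will compare treatments on changes in OCD symptom severity across all measurement periods, with baseline scores as covariates". The plan then gives its expectation, "we expect that both ERP and CT will be similarly effective", and bases it on earlier trials and a review. It adds a qualification, "perhaps with intent-to-treat analyses showing a small advantage of CT over ERP", and closes with the caveat "yet we do not expect to be powered to detect significant differences".

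The Study Protocol section schedules the YBOCS and VOCI after session 6 and at the end of treatment, and "at 6- and 12-month follow-up periods, participants will complete the mid-therapy assessment measures again". That makes four post-baseline visits at which both measures are taken. The VOCI is also completed before every one of the 12 sessions.

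The documents state no sample size, SD, baseline correlation, significance level, margin or method for missing scores. They do not say which measure, time point or analysis set leads.

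**The concern.** The plan expects similarity but names only a test for difference, and it predicts that the test will lack power. The most likely result is therefore a non-significant p-value, which taken alone is limited evidence that two treatments work equally well.

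This would matter to a reader. The Study Protocol section describes ERP as established and highly effective, and describes many elements of this CT as novel and untested in earlier randomised trials of CT. If CT proves more acceptable, the next question is whether it is also less effective. A bare p > 0.05 does not answer that. An adjusted difference with its interval shows which differences the data still allow.

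Choice among results is a second worry. With several measures, time points and two analysis sets, and none designated as lead, a report could favour whichever contrast suited it. The completer and intent-to-treat sets could also disagree, since dropout may differ by arm and is itself a primary outcome.

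**Working it through.** **No planned figure to reproduce.** The documents give no power, sample size or precision statement for symptoms beyond the caveat. The numbers below are illustrations on assumed inputs.

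**Number of contrasts.** Counting only the four assessment visits: 2 measures × 4 visits × 2 analysis sets = 16. This is not an upper bound. The VOCI is also taken before each session. Counting the 11 pre-session scores from session 2 onward adds 11 × 2 = 22, giving 38. If the reference to all measurement periods means one pooled comparison per measure and set, the count falls to 2 × 2 = 4. The wording does not settle which is meant.

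**What a null result would show.** Assumed: YBOCS SD 7, correlation with baseline r = 0.5, two-sided 5%, n analysed per arm, and a 3-point true difference as a yardstick.

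- One time point: SE = SD × √(1 − r²) × √(2/n)
- Mean of four visits, inter-visit correlation assumed 0.7: SE = SD × √((1 + 3 × 0.7)/4 − r²) × √(2/n)
- Half-width = t(0.975, 2n − 3) × SE
- Probability of non-significance at 3 points: non-central t with non-centrality 3/SE

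For n = 30 and one time point: SE = 7 × √0.75 × √(2/30) = 1.565, and half-width = 2.002 × 1.565 = 3.13.

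| | n per arm | SE | 95% half-width | Non-significant if truth is 3 points | 0.95 ÷ that probability |
|---|---|---|---|---|---|
| One time point | 30 | 1.565 | 3.13 | 53% | 1.8 |
| One time point | 60 | 1.107 | 2.19 | 23% | 4.1 |
| Pooled, four visits | 30 | 1.310 | 2.62 | 39% | 2.5 |
| Pooled, four visits | 60 | 0.926 | 1.83 | 11% | 9.0 |

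The last column is the factor by which a null result favours equality over a 3-point difference.

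Over SD 6 to 8 and r 0.3 to 0.7, the probability of non-significance at 3 points is 24–68% (n = 30) and 3–43% (n = 60) at one time point. Pooled, it is 5–59% and 0.1–31%. The evidence in a null result could therefore be weak or fairly strong, and the documents cannot say which.

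**What the planned analysis already provides.** The ANCOVA estimates the treatment difference D and its SE. The p-value comes from D/SE, and the interval is D ± t × SE. Both come from the same fit, so reporting the interval needs no new model, data or participants.

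**What the text claims.** The statement on similar effectiveness is a forecast resting on outside evidence. The next clause concerns power. No sentence links a non-significant result in this trial to a conclusion of similarity.

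**The case for a change.** The strongest case for a change is that admitting low power puts nothing informative in its place. The plan expects a null result, does not say how it will be read, and leaves the lead contrast open. A few sentences written before outcome data are examined would settle this: one intent-to-treat difference with its 95% interval, the rest as supportive, and a statement that p > 0.05 will not be called similarity. The cost is wording only.

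The factual part of this stands. No lead measure, time point or analysis set is named, no interval is promised, and no reading rule is given. Those sentences would be harmless and mildly useful.

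Three things keep it from being a needed correction. First, it guards against a misreading that the plan has not made and has partly forestalled with its own caveat. Second, it leaves the analysis as it is: the same ANCOVA gives the same estimate, and nothing in the documents says which measure or time point ought to lead. Third, naming a lead intent-to-treat contrast would not by itself fix the estimate, because the result also depends on how the missing scores of refusers and dropouts are handled, and that is unstated. Nor is the intent-to-treat set automatically the cautious one for a similarity claim, since participants who received little treatment can pull the arms together.

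**Conclusion.** No change follows. The plan leaves out reporting detail for a non-primary comparison, and following it as written has not been shown to produce a wrong result. Its expectation of similar effectiveness is openly a prior belief, its lack of power is declared, and the estimate and interval that a reader needs come directly from the planned ANCOVA. A competent analyst would report them and would not present a null result as proof of similarity.

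The size is indeterminate. On the assumed inputs, the half-width for YBOCS runs from 1.8 points (pooled, 60 per arm) to 3.1 points (one time point, 30 per arm). A true 3-point difference would be missed 11% to 53% of the time across those same cases. Every one of these figures depends on an assumed SD, correlation, sample size and yardstick, so they show why the interval is worth reading and do not measure a defect in this trial. The judgement would differ if symptom severity were a primary outcome, or if the plan said that non-significance would be taken as similar effectiveness. Neither is the case.
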